Any paper source forms will be stored in a locked cabinet in a locked office at the UCSF Women's Health Clinical Research Center, and only research staff who need to access these forms for data collection, data editing, or quality monitoring purposes will have the key to this cabinet. Information that could identify individual participants will not be released without written permission of the participant, except as necessary for monitoring by the IRB, NIA, the OHRP, or other government agencies responsible for protecting participant safety. Paper-based source forms will be securely destroyed 3 years after the end of the study.

N. ETHICAL CONSIDERATIONS

This research will be conducted in accordance with principles outlined in, "[The Belmont Report: Ethical Principles and Guidelines for the Protection of Human Subjects in Research](#)" (National Commission for the Protection of Human Subjects of Biomedical and Behavioral Research, April 1979), which include respect for persons, beneficence, and justice.

O. STEERING COMMITTEE

The conduct of this research will be overseen by a steering committee composed of the principal and co-investigators—[name]; [name], MPH; [name]; [name]; and [name].

P. PUBLICATION OF RESEARCH FINDINGS

Any publications resulting from this research will be made available to the public consistent with the NIH public access policy. At the request of the NIA program officer, the principal investigator will also provide a copy of any abstracts or manuscripts resulting from this work to the program officer prior to submission.

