To achieve the primary efficacy objective, changes in the frequency and severity of hot flashes will be assessed over 4 and 12 weeks using a validated 7-day symptom diary. To achieve the secondary efficacy objective, changes in other hot flash-related symptoms and quality-of-life outcomes will be assessed using validated questionnaires. To achieve the secondary safety objective, specific potentially severe side effects of NTG will be systematically assessed, and other reported unanticipated adverse events will also be evaluated using standardized forms at all follow-up visits.

This design is designed to provide the first rigorous evidence to evaluate the efficacy and tolerability of uninterrupted NTG for treatment of menopausal hot flashes, while making efficient use of research resources.

E. SELECTION AND ENROLLMENT OF PARTICIPANTS

E.1 Overview

Eligibility criteria are designed to identify peri- or postmenopausal women with frequent and bothersome hot flashes, who are not using other clinical hot flash treatments, have no history of coronary disease or multiple risk factors for coronary disease, and do not have clear contraindications to transdermal NTG therapy. To maximize generalizability, women from multiple menopausal stages will be enrolled, provided they meet all hot flash-related and clinical criteria and complete measurements that can clarify menopausal/hormonal status.

E.2 Inclusion Criteria

- 1) Women aged 40 to 62 years (consistent with the recent MSFlash hot flash network trials, and likely to maximize enrollment of highly symptomatic women)

- 2) Postmenopausal or in the late menopausal transition. For this study, postmenopausal status will be defined by: 1) self-reported history of bilateral oophorectomy, 2) follicle stimulating hormone (FSH) levels > 20 mU/mL for those with a self-reported history of hysterectomy without bilateral oophorectomy, or 3) no self-reported history of hysterectomy or oophorectomy, but absence of menses in the past 12 months. Late menopausal transition will be defined by amenorrhea for at least 60 days in the past 12 months within the specified age group.
- 3) Documentation of an average of 7 or more hot flashes per 24 hours as well as 4 or more moderate-to-severe hot flashes per 24 hours as recorded on a validated 7-day screening symptom diary
- 4) Willing to refrain from initiating other treatments that are known to affect the frequency of severity hot flashes during the trial period

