- 5) Report having a current primary health care provider (such as a general practitioner, family medicine, internal medicine, or nurse practitioner providing primary care or specializing in women's health)

E.3 Exclusion Criteria

- 1) Current or recent use of NTG or other nitrate-containing medications (i.e., use within 1 month of screening), or intention to use nitrate-containing medication during the interventional period
- 2) Current or recent use of medications already known to reduce the frequency or severity of hot flashes (e.g., vaginal or transdermal estrogens in the past 4 weeks; oral estrogens or progestins in the past 8 weeks; intrauterine progestin therapy in the past 8 weeks; progestin implants or estrogen alone injectable therapy in the past 3 months; estrogen pellet therapy or progestin injectable therapy in the past 6 months; clonidine, methyldopa, gabapentin, pregabalin and selective serotonin or norepinephrine reuptake inhibitors (SSRIs/SNRIs) in the past 1 month); or intention to use these medications during the interventional period
- 3) Current or recent use of phosphodiesterase inhibitor medications (within 1 month of screening), or intention to use these medications during the interventional period
- 4) Current or recent use of riociguat, a soluble guanylate cyclase stimulator medication, within 1 month of screening, or intention to use riociguat during the interventional period
- 5) Self-reported history of hypertrophic obstructive cardiomyopathy, aortic valve stenosis, or mitral valve stenosis (since symptoms of these conditions may be aggravated by NTG therapy)
- 6) Self-reported history of coronary disease (since patients with coronary disease may need NTG therapy for chest pain or may be at increased risk of new coronary events in the setting of nitrate tolerance), or evidence of prior myocardial infarction on screening electrocardiogram (ECG)
- 7) Self-reported history of diabetes or 2 or more major risk factors for coronary disease (i.e., smoking, hypertension, or hyperlipidemia with physician-recommended pharmacologic treatment)
- 8) Evidence of tachyarrhythmias such as atrial fibrillation or flutter without adequate rate control (>110 beats/minute) on screening ECG
- 9) Evidence of second or third-degree atrioventricular block on screening ECG

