- 10) Hypotension based on measured resting blood pressure <90/60 at baseline; or normal resting blood pressure but evidence of orthostatic hypotension with change from supine to standing position)
- 11) Uncontrolled hypertension based on measured resting blood pressure > 180/110 at baseline
- 12) Self-reported headaches interfering with activities of daily activities more than twice a month, or use of prescription medication to prevent or treat headache in the past month (since these may be

worsened by NTG therapy)

- 13) Known allergy to nitroglycerin or other nitrate-based medications.
- 14) Known skin sensitivity to adhesives (which may generalize to the NTG patches)
- 15) Unable to complete or tolerate a brief 3-day run-in period involving the lowest available dose of NTG (0.1 mg/hr)
- 16) Currently pregnant, gave birth within the past 3 months, planning pregnancy during the study period, or unwilling to use regular barrier contraception or abstain from sexual activity to prevent pregnancy if not yet postmenopausal
- 17) Currently breastfeeding, breastfeeding within the past 3 months, or planning to breastfeed during the study period
- 18) Self-report heavy alcohol use (>3 drinks in a given day or >7 drinks per week) and uncomfortable or unwilling to decrease their alcohol intake during the study period.
- 19) Unable or unwilling to provide informed consent, fill out questionnaires, or complete study visits in English; unable or unwilling to use remote platforms (i.e., video, telephone, and/or mail-in platforms) to the above if necessary to promote social distancing
- 20) Report other conditions that, in the judgment of the investigators, render potential participants highly unlikely to follow the protocol, including plans to move, substance abuse, significant psychiatric problems, or severe dementia.

E.4 Recruitment and Consent Procedures

E.4.1 Recruitment strategies

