- Candidates will complete questionnaires about their demographic and medical history to determine if they meet criteria related to age, gender, menopausal history, duration/frequency of hot flashes, and exclusionary conditions.
- Over-the-counter and prescription medications will be reviewed to determine if candidates are taking any exclusionary medications.
- Women will be queried about alcohol use, and those reporting >3 drinks in a given day or >7 drinks per week will be asked if they are comfortable decreasing their alcohol intake during the study period to decrease their risk of side effects of NTG therapy.
- Candidates will be asked to complete structured-item self-report questionnaires about sleep quality, anxiety and depression symptoms, and condition-specific quality of life.
- Height, weight, and resting and orthostatic blood pressure and heart rate measurements will be obtained; candidates may be excluded for either high or low blood pressure.

- A urine sample will be collected to rule out pregnancy (for candidates who may still be of child-bearing potential).
- Candidates under the age of 60 who have a history of hysterectomy without oophorectomy will be sent for FSH hormone testing.
- Candidates who have cardiovascular risk factors such as hypertension, hyperlipidemia, or smoking will undergo a screening resting 12-lead electrocardiogram (ECG) administered by a trained clinical coordinator.
- Potentially eligible women will be instructed on completing a 7-day hot flash diary at home to document the frequency and severity of their hot flashes
- Potentially eligible women will also be given a supply of 0.1 mg/hr NTG patches and instructions on using patches during a 3-day run-in period following completion of their 7-day hot flash diary; of note, participants will be specifically instructed to wait until they have completed their 7-day diary before starting to use the run-in NTG medication.
- Women who are not yet postmenopausal will be counseled to refrain from sexual activity or use barrier contraceptives during the study period.
- A Baseline Clinic Visit will be scheduled at least 10 days after the Screening Clinic Visit to review the completed hot flash diary, assess tolerance to the run-in medication, and determine final eligibility.
- Women will be given a list of prohibited medications that they should avoid for the duration of their participation in this study.

C. Baseline Clinic Visit

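### Menopausal stage counts 12 months of amenorrhea whatever its cause, but the hormone, birth and breastfeeding exclusions reach back only 4 weeks to 6 months, so hormone-induced amenorrhea can be labelled postmenopausal and lift the contraception provisions

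*Combined protocol and SAP*

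**What the plan says.** Section E.2, criterion 2, gives three routes to postmenopausal status. Limb 1 is bilateral oophorectomy. Limb 2 is an FSH level above 20 mU/mL after hysterectomy without bilateral oophorectomy. Limb 3 is "no self-reported history of hysterectomy or oophorectomy, but absence of menses in the past 12 months". The other stage is set by one sentence: "Late menopausal transition will be defined by amenorrhea for at least 60 days in the past 12 months within the specified age group". Neither limb 3 nor that sentence asks why menses stopped.

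Section E.3 sets the look-backs that bear on other causes. Criterion 2 lists "vaginal or transdermal estrogens in the past 4 weeks; oral estrogens or progestins in the past 8 weeks", then "intrauterine progestin therapy in the past 8 weeks; progestin implants or estrogen alone injectable therapy in the past 3 months", and 6 months for estrogen pellets and injectable progestin. Criterion 16 begins "Currently pregnant, gave birth within the past 3 months", and criterion 17 uses 3 months for breastfeeding.

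FSH is ordered only for women under 60 after hysterectomy without oophorectomy (G.1.4 D and H.1.3 B), so a woman with a uterus has none.

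The stage label has consequences. The contraception clause of E.3(16) is there "to prevent pregnancy if not yet postmenopausal". H.1.3 B says: "Women who are not yet postmenopausal will be counseled to refrain from sexual activity or use barrier contraceptives during the study period". The reminders with conditional pregnancy tests at baseline (H.1.3 C) and at weeks 1, 2 and 5 (H.2.5) carry the same condition. Stage is also the only stratification factor (H.1.4 B) and a named subgroup factor (K.4.5).

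**The concern.** A definition with a 12-month window is paired with exclusions whose windows are shorter. Amenorrhea from contraceptive hormones, pregnancy or lactation that falls between the two counts toward menopausal stage.

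Through limb 3, a woman who may still be able to conceive can be labelled postmenopausal, and the label switches off protections that the protocol means for women like her. She also enters the wrong stratum. Through the late-transition rule, a woman who is not in the menopausal transition can be judged eligible and placed in that stratum and subgroup.

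Limb 3 also errs the other way. It bars any oophorectomy, not only bilateral, so some women with long-standing amenorrhea cannot be classed as postmenopausal at all.

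**Working it through.** The plan states no figure on this point, so the check compares windows.

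**Step 1: days of the look-back that no exclusion covers.** Formula: 365 minus the exclusion window in days, with one month taken as 30.44 days.

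| Source | Window in E.3 | Days covered | Days left | Share of 365 |
|---|---|---|---|---|
| Vaginal or transdermal estrogen | 4 weeks | 28 | 337 | 92% |
| Oral hormones; intrauterine progestin | 8 weeks | 56 | 309 | 85% |
| Implant; estrogen-alone injectable | 3 months | 91 | 274 | 75% |
| Pellet; injectable progestin | 6 months | 183 | 182 | 50% |
| Birth; breastfeeding | 3 months | 91 | 274 | 75% |

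The shares are of calendar time, not of women, and the table does not claim that each agent stops menses. Every gap exceeds 60 days, so amenorrhea inside any one of them is long enough on its own to meet the late-transition rule.

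**Step 2: postmenopausal label after hormone use.** Premise: some users of an intrauterine progestin do not bleed. Take removal just over 8 weeks ago and no menses since. Limb 3 needs 52 weeks without menses, and 52 − 8 = 44 weeks (about 10 months) must then fall while the device was in place. A woman without bleeding for that long passes the 8-week washout and meets limb 3.

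**Step 3: pregnancy.** Assumption, not in the documents: 280 days without menses before delivery.
- Late transition: a birth 4 months ago (122 days) leaves 365 − 122 = 243 days of pregnancy amenorrhea in the window. The 60-day rule is still met by a birth up to 365 − 60 = 305 days ago, about 10 months.
- Postmenopausal: 280 + 91 = 371 days, just over 365. A woman barely past the birth exclusion meets limb 3 only if she has had no menses since delivery and has not breastfed in the past 3 months. This route is narrow.

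**Step 4: what each label does.** Women classed as late transition are not yet postmenopausal, so the contraception criterion, counselling and conditional tests still apply to them. The exemption arises only through limb 3.

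**Step 5: oophorectomy wording.** Take a woman with a uterus, one ovary removed and years of amenorrhea. Limb 1 fails (not bilateral), limb 2 fails (no hysterectomy), and limb 3 fails (an oophorectomy). She meets the 60-day rule and becomes late transition. In the same way, limb 2 needs an FSH result for a woman with a hysterectomy and one ovary removed, but G.1.4 D and H.1.3 B order the test only when there was no oophorectomy.

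**The case against.** The washouts in E.3(2) are there to remove drugs that suppress hot flashes, not to validate stage, so their shorter length is not in itself a contradiction. That is right. The gap lies in E.2(2), which does not deal with cause, and nothing else in the plan closes it.

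Other safeguards narrow the problem. E.2(3) requires at least 7 hot flashes per day, 4 of them moderate-to-severe. Pilot women with at least 7 per day averaged 51.4 years (SD 4.3; C.3), so a 41-year-old would lie (51.4 − 41)/4.3 = 2.4 SD below that mean. Current or planned pregnancy excludes at any stage. The screening urine test covers women of possible child-bearing potential, whatever their stage label, and the principal investigator confirms eligibility. These points stand and make cases uncommon. They do not remove the gap: child-bearing potential is not defined, one screening test does not restore contraception or later testing, and no rule tells the investigator to discount hormone-induced amenorrhea. Because E.3(2) treats these hormones as reducing hot flashes, a woman who has just stopped one might also reach the threshold; that is an inference.

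A reader might infer that the late-transition sentence itself exempts fertile women from contraception. It does not (step 4). A reader might also infer that limb 3 strips a woman of every pregnancy protection. It does not: the exclusion of current or planned pregnancy and the screening test remain.

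The limb 3 oophorectomy wording errs in the protective direction, since that woman keeps the contraception provisions. Only her stratum and subgroup are wrong.

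**Conclusion.** The concern holds, with limited reach. As written, limb 3 can label hormone-induced amenorrhea as postmenopausal, with 182 to 337 of 365 days uncovered depending on the product. That label removes the contraception criterion, the counselling and the conditional pregnancy tests. The late-transition rule has the same gap, but its effect stops at eligibility, stratum and subgroup. The oophorectomy wording is a separate internal inconsistency.

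The documents give no basis for counting affected women, so none is offered. A reader might infer that the efficacy result is compromised. The documents do not support that: a few women in the wrong stratum do not bias a randomized comparison, K.4.5 calls the subgroup work exploratory, and no stratum has a target size. What is at stake is who is enrolled, how stage is recorded, and whether the pregnancy provisions reach the women they are meant for. The conclusion rests on reading the criteria literally, on the premise that some progestin users do not bleed, and, for the pregnancy cases, on the 280-day assumption.

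**What to change.** - In E.2(2), count amenorrhea toward either stage only when it is not explained by hormone use, pregnancy or lactation during the 12-month look-back. Check this against the menstrual, parity and medication history in G.1.4. That list does not name past contraceptive use, and Appendix A inventories current medications only, so add one question on contraceptive hormones over 12 months if needed.
- Use *bilateral oophorectomy* in limb 3, G.1.4 D and H.1.3 B, to match limbs 1 and 2.
- The investigators should reconcile E.2(2) with the pregnancy provisions of E.3(16) for women whose stage cannot be established, and state how such women are stratified.

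FSH testing is not a ready remedy. The plan's only cut-off applies after hysterectomy, it does not separate late transition from premenopause, and wider testing would add a procedure.

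Cost: one clause, a wording change in three places, a short added history check, and possibly a few exclusions.

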At baseline, mean (\pm SD) age was 51.4 (\pm 4.3) years, 42% of participants were racial/ethnic minorities. The mean frequency of hot flashes at baseline was 10.6 (\pm 2.1) per day, and the mean frequency of moderate-to-severe hot flashes was 7.2 (\pm 3.7) per day. Over 4 weeks of escalating dose treatment, the average daily frequency of hot flashes decreased by 54% to 5.0 (\pm 2.5), and the average daily frequency of moderate-to-severe hot flashes decreased by 69% to 2.3 (\pm 2.6) (P <0.01 for both). Women also demonstrated improvements in scores of 60% on the Hot Flash Daily Interference Scale, 46% on the Beck Depression Inventory, 46% on the Insomnia Severity Index, and 33% on the Menopausal Quality of Life vasomotor domain from baseline to maximum dose therapy (P <.05 for all). During a one-week period after discontinuation of NTG, frequency of any hot flashes increased by 23%, and frequency of moderate-to-severe hot flashes increased by 96% (P <0.01 for both).

Two women developed headache on the initial 0.1 mg/hr patch, leading them to discontinue treatment before the first outcomes assessment. Among women who tolerated the initial dose of TNG, however, none subsequently experienced any serious adverse events or discontinued treatment for side effects. Eleven women opted to escalate to 0.6 mg/hr dose therapy, while three preferred to remain at 0.4 mg/hr and three on 0.2 mg/hr therapy. Average improvement in hot flash frequency from baseline associated with each NTG dose was 28% for 0.1 mg/hr, 34% for 0.2 mg/hr, 39% for 0.4 mg/hr, and 53% for 0.6 mg/hr. Average blood pressure

was 127/79 mmHg, 129 /78 mmHg, 130/81 mmHg, and 125/77 mmHg on 0.1 mg, 0.2 mg/hr, 0.4 mg/hr, and 0.6 mg/hr dose NTG, respectively, and 130/81 mm Hg after discontinuation of NTG.

D. STUDY DESIGN

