Food and Drug Administration 2003, Grady, Sawaya et al. 2009). Participants will be asked to record each hot flash they experience on this diary and rate it as: 1) mild (sensation of heat without sweating), 2) moderate (sensation of heat with sweating, not preventing the participant from continuing with activity), or 3) severe (sensation of heat with sweating, causing cessation of activity); severity definitions will be provided with the diary.

For this study in which the average frequency of hot flashes at baseline will be high (i.e., at least 7 hot flashes per 24-hour period), the study team believes that this type of real-time diary will lead to more accurate assessment of hot flash frequency than alternate diary formats in which subjects only record their hot flashes once or twice a day by retrospectively recalling their hot flashes over the past 12 or 24 hours. To avoid diary fatigue, participants will be asked to complete the diary for a 7-day period before the baseline, 5-week, and 12-week visits only, rather than recording their hot flashes continuously throughout the trial. To facilitate real-time recording, the diary has been designed to be small and portable, so that women can carry it with them throughout the day and keep it at their bedside at night.

In addition to assessing change in frequency of any hot flashes, diary data will be used to assess change in frequency of moderate-to-severe hot flashes as an important secondary outcome. A total hot flash severity score will also be calculated by taking the sum of severity ratings for all hot flashes recorded during each 7-day period.

G.1.2 Other symptom and quality-of-life outcomes (at the screening, 5-week, and 12-week visits)

Additional symptom and quality-of-life outcomes will be assessed using several validated, self-administered, structured-item questionnaires, including:

A. The Hot Flash Related Daily Interference Scale (HFRDIS)

The HFRDIS is a 10-item self-administered questionnaire that assesses the degree to which hot flashes have interfered with participants' activities over the prior week. Interference with each activity is rated on a 10-point scale, and an overall score is calculated as the average of the items. The HFRDIS has been shown to have good internal consistency reliability, construct validity, and sensitivity to change (Carpenter 2001)

B. The Pittsburgh Sleep Quality Index (PSQI) and Pittsburgh Sleep Diary

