headache during the first 24 hours of therapy, but no significant differences in rates of chest pain, syncope, or severe adverse events defined by CTCAE severity grade 3 or higher.

K.2 Data Analyses

K.2.1 Analyses for Objective 1

Analyses to address aim 1 will examine change in average daily hot flash frequency from baseline to 4 and 12 weeks of treatment, measured over 7 days by validated hot flash diaries (Sloan, Loprinzi et al. 2001, Food and Drug Administration 2003). The effect of NTG therapy will be estimated using linear mixed models (LMMs) for the repeated changes, adjusting for baseline values, under the assumption of an approximately constant treatment effects at 4 and 12 weeks; in supplementary analysis we will assess evidence for differences in the treatment effects at these two time points. The distribution of the LMM residuals will be assessed using Q-Q plots, and outcomes will be transformed if necessary to achieve approximate normality. Analyses will be by intention to treat, according to treatment assignment, and without regard to adherence.

K.2.2 Analyses for Objective 2

For additional confirmation of treatment effects on frequency of any hot flashes, we will also assess treatment effects on moderate-to-severe hot flashes and on total hot flash severity scores as secondary outcomes, also assessed by diary, using the same methods. The distribution of the LMM residuals will again be assessed using Q-Q plots, and outcomes will be transformed if necessary to achieve approximate normality. Analyses will again be by intention to treat, according to treatment assignment, and without regard to adherence.

K.2.3 Analyses for Objective 3

Analyses to address aim 2 will examine changes in sleep quality and duration, anxiety and depressive symptoms, and menopausal quality-of-life from baseline to 4 and 12 weeks. These outcomes will be captured by scores on validated self-administered questionnaires, with supplementation by sleep diary in the case of sleep duration. Intervention effects on these outcomes will be estimated using LMMs, adjusted for baseline scores. Approximate normality of the residuals will be checked using Q-Q plots, and outcomes will be transformed if necessary. Analyses will once again be by intention to treat and without regard to adherence.

K.2.4 Analyses for Objective 4

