To assess tolerability and safety of NTG, we will compare group-specific rates of: 1) severe symptoms that are potentially attributable to NTG therapy (i.e., headache limiting activities of daily living, chest pain or tightness limiting activities of daily living, or syncope/fainting); and 2) any adverse events with a severity rating of 3 or higher on the CTCAE severity scale (National Cancer Institute 2009). We will also examine group-specific rates of all adverse events, regardless of severity and of anticipated relationship to NTG therapy. Inferences for rare outcomes will be obtained using Fisher's exact test. Because intention-to-treat analysis is conservative, any suggestive differences in safety outcome rates will be assessed accounting for adherence, final dose, and their interactions with treatment.

K.3 Sample Size Determination

Sample size calculations are based on parameter estimates from prior pharmacologic hot flash trials conducted by the investigators such as the FAST(Grady, Cohen et al. 2007) and CHIMES trials (Grady, Sawaya et al. 2009), which had similar eligibility criteria with respect to age, hot flashes, and treatment history. We assume the study sample will be characterized by: a) mean baseline hot flash frequency of >9 hot flashes/day; b) mean reduction in hot flash frequency in the control group of <3 hot flashes/day (i.e., <33%); c) standard deviation of change in hot flash frequency of ~4.5 hot flashes per day; and d) correlation between baseline and follow-up values of ~0.55.

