Under these assumptions, a sample size of 140 (70 per group) should provide an estimated 87% power in 2-sided tests with type-I error of 5% to detect an 20% greater reduction in hot flash frequency (or 1.8 hot flashes per day) in the active treatment arm relative to the control arm. This will correspond to a 50-55% decrease in hot flash frequency from baseline in the active treatment group, which has previously been described as a clinically important effect in prior hot flash research (Butt, Deng et al. 2007). Estimates account for correlation of the repeated measures and loss to follow-up of up to 15%, and indicate that power will remain $\geq 80\%$ even if actual effect size or other parameters are less favorable than expected. This sample of 70 per group will also provide $>80\%$ power in 2-sided tests with type-I error of 5% to detect a between-group difference in mean frequency of moderate-to-severe hot flashes of ~ 1.5 hot flashes per day, as well as ~ 3.3 points in hot flash severity scores.

K.4 Additional Statistical Considerations

K.4.1 Drop-out rates

Based on past experience, participant dropout levels are expected to remain under 15% over 12 weeks. The assumption of non-informative dropout will be examined by comparing the baseline characteristics and early post-randomization outcomes of participants who are lost to follow-up versus retained in the study. If drop-out rates differ substantially between groups, analyses will be adjusted for baseline covariates associated with retention. In sensitivity analyses, we will also use multiple imputation of missing outcomes under plausible informative missingness assumptions, along with standard methods for calculating summary estimates and confidence intervals, to assess the potential impact of loss to follow-up on treatment effect estimates (Schafer 1999).

K.4.2 Dose effects

In the event that an overall treatment benefit is detected over 12 weeks, we will conduct exploratory analyses to probe for differences in the magnitude of treatment effects by highest-achieved NTG dose, by testing for interaction between treatment assignment and highest-achieved NTG dose in a linear mixed model for change in hot flash frequency. This analysis will control for the main effect of highest achieved dose to control the placebo effect of this self-selected variable, as well as baseline factors that may confound it, such as age, body mass index, and baseline hot flash frequency or severity.

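### The severity score is defined as a 7-day sum, but its detectable difference of about 3.3 points has no time base and is credible only as points per day

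*Combined protocol and SAP*

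**What the plan says.** Section G.1.1 asks women to record each hot flash over 7 days and "rate it as: 1) mild (sensation of heat without sweating), 2) moderate" or severe, so every flash carries 1, 2 or 3 points. The total severity score is obtained by "taking the sum of severity ratings for all hot flashes recorded during each 7-day period". No section divides this sum by days; B.2 and K.1 call the score cumulative, and K.2.2 calls it total.

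Frequency is handled differently. K.2.1 analyses "average daily hot flash frequency from baseline to 4 and 12 weeks of treatment, measured over 7 days", which is a daily average.

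K.3 gives 87% power with 70 women per group for a "20% greater reduction in hot flash frequency (or 1.8 hot flashes per day"). It then claims more than 80% power for a difference in moderate-to-severe flashes of about "1.5 hot flashes per day, as well as" about "3.3 points in hot flash severity scores". The first of these two secondary figures is per day. The second has no time base. No SD, baseline mean or expected change is given for the score.

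**The concern.** The score is one of two diary-based secondary outcomes under Objective 2, and 3.3 points is its only planning figure. A reader who applies the G.1.1 definition will take 3.3 as points on the 7-day sum. If the figure was calculated per day, an observed difference of about 3 points on the defined score would look like the planned detectable effect when it is about one seventh of it.

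**Working it through.** **Inputs.** K.3: 1.8 flashes/day at 87% power, two-sided 5%, 70 per group, up to 15% loss (70 × 0.85 = 59.5 per group), "standard deviation of change in hot flash frequency of" about 4.5 per day, baseline to follow-up correlation about 0.55; about 1.5 moderate-to-severe flashes/day and about 3.3 points at more than 80% power. G.1.1: ratings of 1 to 3. C.3 (pilot): 10.6 flashes/day at baseline, and "the mean frequency of moderate-to-severe hot flashes was 7.2" per day. Assumed because the plan does not give them: the correlation r between the two follow-up diaries, and a score SD equal to frequency SD × mean points per flash.

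**1. Reproducing the 87%.** Single-value SD = 4.5/√(2 × (1 − 0.55)) = 4.743. Baseline-adjusted SD of the mean of two follow-ups = 4.743 × √((1 + r)/2 − 0.55²). With r = 0.55 this is 3.26 and power is 85.3%; with r = 0.50 it is 3.17 and power is 87.2%. The primary figure is reproduced on the per-day scale.

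**2. Comparison within the same sentence.** A moderate-to-severe flash carries 2 or 3 points.

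| 1.5 moderate-to-severe flashes/day | Points per day | Points per 7 days |
|---|---|---|
| Flashes disappear (2 to 3 points each) | 3.0 to 4.5 | 21 to 31.5 |
| Flashes become mild (1 to 2 points each) | 1.5 to 3.0 | 10.5 to 21 |

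On the 7-day sum, 3.3 points is 3.3/7 = 0.47 points per day. It falls well below both weekly ranges. Per day, 3.3 lies inside the first range and a little above the second.

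**3. Comparison with the stated power.** The 80%-power difference implied by 87% power for 1.8 is 1.8 × (1.960 + 0.842)/(1.960 + 1.126) = 1.63 flashes/day. This needs no frequency SD, correlation or dropout figure.

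- Per day: 3.3/1.63 = 2.02 points per flash.
- Per 7 days: 3.3/(7 × 1.63) = 0.29 points per flash, below the lowest possible rating of 1.

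Pilot mean severity at baseline lies between (7.2 × 2 + 3.4)/10.6 = 1.68 and (7.2 × 3 + 3.4)/10.6 = 2.36, where 3.4 = 10.6 − 7.2 mild flashes. The value 2.02 is inside that range. With the model of step 1 it is 2.02, 1.97 and 1.83 for r = 0.50, 0.55 and 0.70.

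**4. Power for 3.3 points on the 7-day sum.** With r = 0.55, the standard error of the group difference in frequency is 3.26 × √(2/59.5) = 0.598 per day. For the weekly score it is 7 × 0.598 × points per flash.

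| Points per flash | Standard error, 7-day sum | Power for 3.3 points |
|---|---|---|
| 1 (all mild) | 4.18 | 12% |
| 1.68 | 7.03 | 8% |
| 2.36 | 9.88 | 6% |

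**5. Conversion.** 3.3 points/day × 7 = 23.1 points on the 7-day sum. The pilot baseline is 17.8 to 25.0 points/day, or 125 to 175 per 7 days. So 3.3 is 13% to 19% of baseline if per day, and 1.9% to 2.6% if per 7 days.

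**The case against.** The strongest reply is that the number is right and only a label is missing. The 3.3 points follow a per-day figure in the same sentence, the other frequencies in K.3 are per day, and K.2.2 uses the methods of K.2.1, which works on daily averages. No success criterion, clinically important difference or stopping rule is tied to 3.3, and the sample size rests on the primary outcome. All of this stands, and it makes an omitted time base more likely than a miscalculation. It does not override the explicit definition in G.1.1, under which the power statement does not hold.

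The checks also have limits. Step 2 sets two detectable differences side by side, although each depends on its own SD, and the per-day match weakens if flashes are only downgraded. Steps 3 and 4 rest on an assumed link between the SDs of score and frequency, and the pilot range comes from 19 women. They are good evidence against the weekly reading and weaker confirmation of the daily one.

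A reader might infer three stronger things that the documents do not support:

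- That the trial is underpowered for severity. Dividing a complete 7-day sum by 7 changes neither the test nor its true power; the 6% to 12% in step 4 concerns only a difference of 3.3 on the weekly scale.
- That K.3 is proven to be too small by a factor of seven, or that the all-mild case (7 × 1.63 = 11.4 points) is a strict lower bound. Without an SD for the score, the first is an inference and the second depends on an assumption.
- That blank diary days are counted as zero. No section says so.

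**Conclusion.** The detectable difference stated for a named secondary outcome is wrong on the scale on which that outcome is defined. A weekly 3.3 points conflicts with the companion figure in its own sentence (10.5 to 31.5 points per week) and with the stated primary power (0.29 points per flash).

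That 3.3 means points per day is the likely explanation but remains an inference. If it holds, the defined score needs about 23 points, and the 3.3 itself needs no recalculation. The consequence is limited to how the planned effect, and later the result, is read.

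**What to change.** First confirm the time base of 3.3 against the original power calculation. If it is per day, choose one of two options:

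- Keep the 7-day sum in G.1.1 and restate the K.3 figure as about 23 points. This changes one number.
- Define the score in G.1.1 as the average daily sum of ratings, in line with the average daily frequency in K.2.1, and state about 3.3 points per day in K.3. This changes one phrase and adds one time base.

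Either way, state the SD assumed for the score. If the daily average is taken over days recorded, say so as a deliberate small change to the outcome: it alters the score for incomplete diaries, where a raw 7-day sum falls with each unrecorded day. Data collection, the analysis model and the sample size stay as they are.
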